Throughout the stay at the Metabolic Unit study volunteers will receive an isocaloric, caffeine-free diet with the following macronutrient distribution: 50% carbohydrate, 20% protein, 30% fat. A research dietitian will meet with participants during the screening visit to plan the isocaloric equilibration diet and to assess food allergies and intolerances. Approximate total energy needs for weight maintenance will be calculated using the Mifflin-St.Jeor equation (27). During two of the metabolic chamber stays study volunteers will be randomized to receive an isocaloric high fat or fat free meal. After an 18 hour resting period the subjects will be crossed over to the second type of meal. Both of the meals will consist of a shake with approximately 600 calories. The high fat meal will contain 50 grams of fat and will have an approximate macronutrient distribution of 72% fat, 8% protein, and 20% carbohydrate. The fat free meal will contain 0 grams of fat and will be 100% carbohydrate. The shakes to be consumed in ≤ 15 min, will be similar in volume and will be served at room temperature.

Body composition

A DEXA scan and an air-displacement plethysmography body composition analysis (BodPod) will be performed at either day 1 or 2 of the hospital stay.

Metabolic chamber

Study volunteers will enter the metabolic chamber at 08:00 AM after a 10-hour fast, voiding, and ingestion of the core temperature probe. Superficial skin temperature probes will also be placed (see below). Study volunteers will wear a standard suit (hospital scrub) and will be allowed to perform regular physical activity while in the metabolic chamber.

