The respiratory chamber is a specially constructed room to assess the metabolism of subjects for a period of 6 hours in this study under constant thermoneutral condition ($73.5 \pm 0.5^\circ \text{F}$). Designed as a walk-in “pull” calorimeter, it is an open circuit unit that draws conditioned room air into the chamber at the same flow rate as it is extracted into the gas analysis system.(28) The room is equipped with toilet and sink with privacy screen, treadmill, bed, desk, and computer with access to television and other forms of entertainment. Physical activity level is measured continuously through a wall mounted monitoring device (microwave sensor). Food and fresh water is passed through an air-lock drawer system. Using this rapid response chamber, we will first measure the resting EE after the patient enters the room. While still fasted, the subject will lie in supine posture and with minimum movement for 30 minutes. After each meal, the subject will be instructed to remain sedentary for 2 hours where the postprandial thermogenesis (EE above the resting level) will be determined. The energy cost of spontaneous physical activity (29) will also be assessed. The respiratory quotient (RQ), as determined by the ratio of carbon dioxide excretion and oxygen consumption, during resting, post-prandial, and overall 6-hour periods will be used to estimate whole-body carbohydrate and fat oxidation rates.

The following parameters will be recorded:

Spontaneous movements

Spontaneous physical movements will be quantified with minute-to-minute resolutions during the study periods using small, portable pager-type and watch accelerometers at the subjects’ hip and wrist (30).

Real-time core and skin temperature

The VitalSense® monitor (Mini Mitter/Respironics, Bend OR) is used to receive transmissions from multiple miniature, wireless, temperature sensors. Core temperature is sensed by the ingestible Jonah™ capsule. Dermal temperatures are recorded from hypoallergenic, non-irritating, adhesive dermal patches. Both sensor types are disposable, but designed for multi-day use under demanding physical and environmental conditions. Both types of sensors use low-power radio frequency transmissions to communicate with the Monitor. The core temperature capsules transmit at various frequencies, therefore, it is possible to track more than one capsule at a time.

Blood sampling, urine collection

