This study, aimed to analyze the role of BAs in postprandial thermogenesis, is not a therapeutic trial. Research-related risks in this study include those associated with study procedures, namely blood drawing. We do not expect serious study medication-related risks except nausea or mild and transient diarrhea (see below) due to the single injection of sinalide or to a single dose of ursodiol, nor do we expect any significant risk connected to the respiratory chamber stay.

Metabolic Chamber.

Besides inconveniences that can reasonably be expected as a result of spending 6 hours in the live-in room calorimeter, the serious risk to subjects' health is minimum.

Blood drawing.

The placement of intravenous needles may cause transient pain, and occasional infection or bruising at the insertion site. Study subjects will undergo 5 venipunctures (14 blood draws during each metabolic chamber stay) during the study. Each blood drawing will be for 5 mL of blood. However, in compliance with NIH guidelines, no more than 6 mL/Kg will be drawn from any study participants during a six-week period.

Core-body and surface temperature measurements.

A small temperature "pill" and wireless surface patches (VitalSense, Mini Mitter, Bend OR) will be used to measure the diurnal variation of body temperature, and a small receiver will need to remain close to the body. The "temp pill" is a capsule (8.7 mm x 23 mm) which is swallowed with water and will be stay in the digestive tract for 2-3 days until being eliminated in the feces. Patients are advised not to undergo MRI procedure until the capsule is passed. No other known side-effect has been reported.

Frequent blood-pressure monitoring.

An ambulatory blood pressure monitor (Oscar 2, SunTech Medical, Morrisville NC), using a cuff on the upper arm, will be programmed to measure BP every 15 minutes. During the measurement, temporary pressure/restriction to the arm is typical. Minor pain may be experienced if the cuff is too tight. Adjustment of the cuff is allowed. No other known side-effect has been reported.

DEXA Scan.

The use of DEXA scan apparatus may cause some minimal discomfort in claustrophobic subjects and may cause some minimal back pain in a small minority of the individuals.

Radiation Safety.

The radiation exposure of a whole-body DEXA Scan is less than 1 mrem. A typical radiation dosage from a chest X-ray is 20 mrem. A normal individual is exposed to 300 mrem/year from natural sources.

Study drugs:

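### The protocol sets no minimum interval between swallowing the core-temperature capsule and the room-temperature shake, so early post-meal core readings may reflect the drink

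*Combined protocol and SAP*

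**What the plan says.** The Metabolic chamber section gives the order of events: "Study volunteers will enter the metabolic chamber at 08:00 AM after a 10-hour fast, voiding, and ingestion of the core temperature probe". Then comes the resting measurement: "While still fasted, the subject will lie in supine posture and with minimum movement for 30 minutes". No other timed step before the meal is described.

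Under Metabolic Diet, the two shakes are drunk in 15 minutes or less and "will be similar in volume and will be served at room temperature". Their volume in millilitres is not given. After the meal: "After each meal, the subject will be instructed to remain sedentary for 2 hours". This is the window for postprandial thermogenesis (PPT), defined there as energy expenditure above the resting level.

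The section on real-time core and skin temperature names one core sensor: "Core temperature is sensed by the ingestible Jonah™ capsule". It describes the sensors as suited to multi-day use and adds that "it is possible to track more than one capsule at a time". The risk section says the capsule "will be stay in the digestive tract for 2-3 days until being eliminated in the feces".

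The opening summary lists core temperature among the parameters to be recorded and compared with placebo. Under Statistical analysis, the primary endpoint is change in energy expenditure.

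The readable text gives no minimum time from swallowing to intake, no check that the capsule has left the stomach, no rule for early post-meal readings, and no rule on which capsule is read when two are present.

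**The concern.** A capsule in the stomach measures gastric contents. If about 600 kcal of liquid at room temperature arrives while it is there, the trace falls for a reason unrelated to metabolism. The fall runs opposite to the rise that thermogenesis would produce, and it comes in the first part of the same 2-hour window.

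Hypothesis 1 compares the response to sincalide or oral bile acid with the response to a high-fat meal. For core temperature, that sets stays with a large cool drink against stays for which no shake is described. An artefact confined to the meal stays does not cancel in that comparison.

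It could also vary by period. The second meal stay follows 24 hours after the first (6-hour stay plus 18-hour rest), so a day-old capsule may still be present. Some volunteers might then be read from the old capsule and others from a new one.

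**Working it through.** No figure in the plan depends on this point, so there is none to reproduce. The check has three steps.

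**1. Can the capsule and shake meet?** Let L be the lead time from swallowing to chamber entry (not stated) and R the time the capsule spends in the stomach (not stated; 30 to 300 minutes assumed). The shake arrives 30 minutes after entry at the earliest; I take 60 minutes as an assumed upper value. They meet if R > L + 30 (early shake) or R > L + 60 (later shake).

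| L (min) | R = 30 | R = 60 | R = 120 | R = 240 | R = 300 |
|---|---|---|---|---|---|
| 0 | no | early shake only | yes | yes | yes |
| 60 | no | no | early shake only | yes | yes |
| 120 | no | no | no | yes | yes |
| 300 | no | no | no | no | no |

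Same-morning swallowing leaves the capsule exposed over much of the assumed range. A lead of 300 minutes removes the problem within it. The blood-sampling scheme (−15 to 360 minutes within a 6-hour stay) also suggests that intake comes soon after entry, if time zero is intake. That is an inference.

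**2. How large is the gap at mixing?** The chamber is held at 73.5 °F: (73.5 − 32) × 5/9 = 23.1 °C, used as a proxy for the shake. With V mL of shake (200 to 600, assumed) and S mL of gastric contents at 37 °C (25 to 200, assumed):

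T = (V × 23.06 + S × 37)/(V + S)

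- V = 200, S = 200: 30.0 °C, or 7.0 °C below 37 °C.
- V = 400, S = 100: 25.8 °C, or 11.2 °C below.
- V = 600, S = 25: 23.6 °C, or 13.4 °C below.

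**3. How long does it last?** Assume exponential rewarming with a half-time h of 5 to 20 minutes. The time for a deficit d to fall below 0.2 °C is h × log2(d/0.2).

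- d = 7, h = 5: 5 × log2(35) = 26 minutes.
- d = 13, h = 20: 20 × log2(65) = 120 minutes.

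So the artefact lasts about 25 to 120 minutes. For a capsule that remains in the stomach, the mean error over the 2-hour window is about d × h/(0.693 × 120). This is 7 × 5/83.2 = 0.4 °C at the low end and 13 × 20/83.2 = 3.1 °C at the high end. If a true postprandial change is a few tenths of a degree (assumed), even the low end is comparable with it.

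**The case against.** The strongest reply is that the sentence on chamber entry gives sequence only. One item in its list, the 10-hour fast, began the evening before, so the capsule might have been swallowed well ahead too. Figure 2, which covers the procedures of each stay, is not shown in the text reviewed and may give the time. A fresh capsule every morning is not stated either: with multi-day sensors and consecutive stays, an earlier capsule may already be the one read. Gastric residence, shake volume and rewarming rate are all assumed, and a drop of several degrees would be obvious in a real-time trace.

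Much of this stands. A reader might infer that the protocol orders ingestion immediately before entry. It does not; same-morning ingestion is only the natural reading. What remains is that no readable passage requires a lead long enough to avoid the problem, or says which capsule counts.

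Three other stronger readings also fail:

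- **That PPT or the primary endpoint is biased.** Both rest on calorimetry, not on the capsule.
- **That the fat versus carbohydrate contrast is invalid.** The shakes share temperature and approximate volume, so most of the artefact cancels. Only a difference in gastric emptying could leave a remainder, and the documents give no figure for that.
- **That core temperature is wrong by 7 to 13 °C.** That is the value at the moment of mixing, and it fades.

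Visibility in the trace helps with large drops. It does not help with the tail, where a residual of a few tenths of a degree looks like physiology and no rule says where to cut.

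**Conclusion.** The point holds as a gap in the measurement procedure for a listed outcome that is not primary. If the capsule is swallowed on the morning of a meal stay and is still in the stomach at intake, part or nearly all of the 2-hour post-meal core-temperature record is unreliable. Later readings in the 6-hour stay can remain usable. The exposed comparison is mainly meal stays against placebo or drug stays.

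The size rests on assumed gastric residence, volumes and rewarming half-time, with chamber temperature standing in for shake temperature. The number of volunteers affected cannot be derived from the documents. The change is worth making because it is nearly free and the lost readings cannot be recovered reliably afterwards.

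**What to change.** In the Metabolic chamber section:

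- Have the capsule swallowed the evening before the first chamber stay, before the 10-hour fast begins. With entry at 08:00 that means by 22:00, so at least 600 + 30 = 630 minutes before the shake, against an assumed upper residence of 300 minutes.
- On later stays, analyse a capsule swallowed no later than the previous evening, while it still transmits. Check transmission each evening and replace the capsule then if it has passed.
- Record the swallowing time and the identity of the capsule analysed.
- If only a same-morning capsule is available, flag its readings and exclude those from the early period after oral intake until the trace has recovered, by a criterion fixed in advance. Do not discard the whole post-intake record.

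The cost is a changed ingestion time for volunteers who are already inpatients. By the protocol's own 2 to 3 days in the gut, a capsule swallowed at 22:00 covers the first two stays (the second ends 10 + 24 + 6 = 40 hours later) and possibly the third (64 hours). Two or three capsules would then nominally serve all five stays. The downside is that an occasional capsule will pass early and need replacing.

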This natural history research protocol is designed as a double blind-cross over study with both pharmacological and nutritional interventions. During a seven-day stay at the NIH, volunteers will undergo five 6-hour clinical and experimental observations in the metabolic chamber. The timing of the experiments have been based on the observations of Hoffman and colleagues who have shown that the peak of BA's occurs at ~2 hours postprandially in a physiological pharmacokinetic model in man (25) and of Foberg et al. who showed that CCK induced a rise in serum bile acids (3 α -HBA) peaked at ~30 minutes and returned to baseline within 120 min (6). The overall outline of the study is reported in Figure 1. Briefly, eligible volunteers will be invited for a seven-day stay at the Metabolic Unit. After a two-day isocaloric equilibration diet, study volunteers will be randomly assigned to receive either a very low or high-fat isocaloric standardized liquid meal during a 6-hour stay in the metabolic chamber. After an 18-hour resting period the volunteers will then be crossed-over to the second type of meal. After an 18-hour resting period the volunteers will again be randomly assigned to receive an IV injection of sincalide (*Kinevac*, a sterile lyophilized powder of the C-terminal octapeptide fragment of cholecystokinin) 0.04 mcg/kg or placebo during a 6-hour stay in the metabolic chamber. After an 18-hour post infusion resting period, the volunteers will be crossed-over to the alternate study arm; during these two interventions the volunteers will also receive a P.O. placebo. The next day, after an 18-hour post infusion resting period from the previous metabolic chamber stay, the volunteers will receive an IV infusion of placebo and 15 mg/kg of ursodiol (as 300 mg capsules rounded up to the nearest 300 mg), and will undergo the same recording. The volunteers will be blinded relative to the composition of the IV and PO compounds. This study design is necessary to avoid carry-over effects of the PO BAs.

[figure not shown]
Fig. 1 Study protocol, overview

Equilibration diet: 2 days; Metabolic chamber stay: 6-hours

During each 6-hour stay in the metabolic chamber we will record the following parameters and will perform these procedures (Fig. 2, **A**: High fat/High carbohydrate meal, **B**: Sinicalide/IV Placebo-P.O. Placebo, **C**: IV Placebo-ursodiol):

Fig. 2 6-hour Metabolic Chamber stays, procedures and blood drawing protocol

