Subjects will be screened and counseled at the initial screening visit. After obtaining informed consent, the study volunteers will undergo a history and physical examination, and the following screening tests will be performed, including: TSH, glucose, creatinine, AST, ALT, CBC, cholesterol, EKG and gall bladder ultrasound. Subjects are required to fast for at least 12-hour prior to the laboratory testing, but will be allowed to drink water during the fasting period. During the screening visit, the study participants will be interviewed by a dietitian in order to assess the caloric intake and food preferences of each study participant.

Hospital stay

Study volunteers will be housed in the Metabolic Unit of the NIH Clinical Center. Non-menopausal female volunteers will be admitted during the early follicular phase (day 2-5) of the menstrual cycle and a pregnancy test will be performed at admission. During the hospital stay, the volunteers will be asked not to perform strenuous physical activity and to abstain from tobacco use. After two days of equilibration diet the subjects will be randomly assigned to receive low and high fat meal during the metabolic chamber stay. The next day the volunteers will receive the alternate meal. The following day the volunteers will be again randomized to sinalide or placebo and P.O. placebo; the next day volunteers will receive the alternate treatment. In the last day of hospital stay the volunteers will again receive IV placebo and 15 mg/kg of ursodiol.

Metabolic Diet

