The primary endpoint of this mechanistic study is the analysis in changes in energy expenditure in response to changes (pharmacological or diet-induced) in serum bile acids concentration. The data will be analyzed using Analysis of Variance (ANOVA) and, should the data suggest an interaction, we will explore statistical models including delta in bile acid concentration, thyroid hormone concentration, and macronutrient diet (as a categorical data). Power analysis: Although this is a pilot study, we use previously published data comparing the effect on PPT (31) to help power the study, The PPT was 7.6-10.1% of the total energy intake, with a standard deviation of 2.6%. If we detect a desired difference of 2.0% in PPT with CCK or high fat diets, 28 study subjects will be needed to provide an 80% statistical power (α error of 0.05, using a two-tailed independent t-test design). We plan to enroll 30 volunteers considering the possibility of missing values.

Research use, storage, and disposition of human subject's samples and data

Serum, plasma, and nucleic acid samples will be coded and stored in a -80°C refrigerator located in the PI's laboratory. Tissue samples will be coded and stored in a liquid nitrogen tank located in the PI's laboratory. A registry of the samples location will be kept in the PI's office. This will allow the PI and the AIs to analyze research data in relation to clinical data stored in the Medical Record Department. Data and samples will be retained for the foreseeable future in order to allow secondary analyses after the completion of the protocol. Such analyses include association studies for known mutations of genes involved in the energy, carbohydrate, thyroid hormone and glucose metabolism, as well as gene scanning for novel mutations. Serum, plasma and nucleic acids samples will be similarly utilized for future association studies of known and novel markers of energy, carbohydrate, thyroid hormone and glucose metabolism. The PI will inform the IRB in case of loss of data/samples secondary to intrusion in the laboratory or database.

Possible Risks and Hazards:

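### Minor: the power statement rests on an independent two-sample t-test, but the meal and sincalide comparisons are both within-subject crossovers; restate the basis and keep enrolment at 30

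*Combined protocol and SAP*

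**What the plan says.** The Statistical analysis section takes its planning values from a published study of postprandial thermogenesis (PPT): "The PPT was 7.6-10.1% of the total energy intake, with a standard deviation of 2.6"%. It sets a target difference of 2.0% in PPT for CCK or high-fat diets and concludes that "28 study subjects will be needed to provide an 80% statistical power (α error of 0.05, using a two-tailed independent t-test design"). Thirty volunteers are to be enrolled to allow for missing values. The calculation is introduced with the words "Although this is a pilot study". The planned analysis is an ANOVA, with no subject or period term mentioned.

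The design is described differently elsewhere. Study design and methods calls the trial "designed as a double blind-cross over study with both pharmacological and nutritional interventions" and crosses volunteers over between the two meals and then between sincalide and placebo. Hospital stay says of the first pair: "The next day the volunteers will receive the alternate meal". Metabolic Diet says: "During two of the metabolic chamber stays study volunteers will be randomized to receive an isocaloric high fat or fat free meal".

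**The concern.** An independent two-sample t-test compares two separate sets of people. Here one set of people supplies both values in each comparison, so the precision of the contrast depends on the SD of the within-subject difference. The plan gives neither that SD nor a within-subject correlation, and it does not say whether 2.6 is the SD under one condition or the SD of a difference.

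This is the plan's only sizing statement. As written, a reader cannot tell how much variability the claimed 80% tolerates. The sentence also covers the CCK contrast, so the mismatch is not confined to the meals. And because the ANOVA is not said to include a subject term, the independent-groups thinking could carry into an analysis that ignores the pairing.

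**Working it through.** **Inputs from the Statistical analysis section.** Difference δ = 2.0 points of PPT; SD = 2.6 points; two-sided alpha 0.05; power 80%; 28 subjects needed, 30 enrolled. The documents give no within-subject correlation ρ. The values 0, 0.3 and 0.5 used below are assumptions made for this review.

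**Step 1: reproduce the 28.**
- Normal approximation, n per group = 2 × (1.960 + 0.842)² × (2.6/2.0)² = 26.5, so 27.
- Exact noncentral t: 27.52, so 28 per group, with power 80.7%.
- The plan's 28 is therefore reproduced as a per-group number. The named test would need 2 × 28 = 56 people.

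**Step 2: paired calculation for the meal comparison.** The noncentrality is δ√n / SD_diff, with n − 1 degrees of freedom. For 80% power it must be about 2.906 at n = 28 and 2.899 at n = 30. The largest SD of the difference that still gives 80% is:
- n = 28: 2.0 × √28 / 2.906 = 3.64 points.
- n = 30: 2.0 × √30 / 2.899 = 3.78 points.

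These two limits do not depend on how 2.6 is read. A period term (n − 2 degrees of freedom) leaves both unchanged to within 0.01.

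**Step 3: the two readings of 2.6.**
- *2.6 is the SD of the within-subject difference.* Power is 97.5% with 28 and 98.3% with 30.
- *2.6 is a single-condition SD.* Then SD_diff = 2.6 × √(2(1 − ρ)):

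| ρ (assumed) | SD_diff | Power, n = 28 | Power, n = 30 |
|---|---|---|---|
| 0 | 3.68 | 79.2% | 82.1% |
| 0.3 | 3.08 | 91.2% | 93.1% |
| 0.5 | 2.60 | 97.5% | 98.3% |

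On this second reading the limits in step 2 correspond to ρ = 1 − 3.64²/(2 × 2.6²) ≈ 0.02 with 28 and 1 − 3.78²/(2 × 2.6²) ≈ −0.06 with 30.

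**Step 4: what ignoring the pairing would cost.** I simulated 400,000 trials per setting with 28 volunteers and a single-condition SD of 2.6, analysed as if the two sets of values were independent. At ρ = 0.3, power is about 85% (paired: 91%) and the true type I error about 2%. At ρ = 0.5, power is about 88% (paired: 97.5%) and the type I error about 0.7%.

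**Step 5: sincalide versus placebo.** This contrast is also within-subject, but no figure can be computed for it from the documents. The 2.0 and 2.6 are on the scale of PPT as a percentage of energy intake. Metabolic chamber ties PPT to a meal: "After each meal, the subject will be instructed to remain sedentary for 2 hours where the postprandial thermogenesis (EE above the resting level"). The text describes test meals in only two of the five chamber stays. Figure 2, which sets out the procedures for each stay, is not shown in the text available.

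**The case against.** The strongest defence is that the label is wrong but the number does no harm. Twenty-eight crossover volunteers supply 28 values per meal. At zero correlation the independent-test variance equals the paired variance, so using it is a cautious choice when no correlation is known. The plan presents the study as a pilot. All of this stands, and it is why the point is minor.

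Two stronger readings are tempting, and neither is supported. A reader might infer that the study needs 56 volunteers, or that 28 people split into two groups of 14 would have only about 50% power. No section describes parallel groups, so neither figure applies to this trial. A reader might also infer that the sincalide comparison certainly has no valid PPT scale. The text points that way, but whether those stays include a meal may be settled by Figure 2, so the request to the sponsor has to be conditional.

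It is also fair to object that assumed correlations should not become protocol text. The fix therefore relies on the tolerated SD, which needs no correlation.

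**Conclusion.** Wrong as written, and minor. The independent t-test does not describe this design for either contrast that the power sentence names, and the plan does not say which SD 2.6 is. The trial is not shown to be underpowered. For the meals, 28 completers suffice for a 2.0-point difference unless the SD of the within-subject difference exceeds 3.64 points, and 30 suffice up to 3.78. If 2.6 is a single-condition SD, power with 28 falls below 80% only when the correlation is about zero or negative, and with 30 only when it is below about −0.06.

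This rests on the plan's own difference, SD and alpha, on a paired t-test, and on 28 to 30 completers. It gives no assurance about sincalide versus placebo, in either direction.

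**What to change.** 1. Replace the independent t-test with a within-subject (paired) calculation, and say whether 2.6 points is a single-condition SD or the SD of the within-subject difference. Possible wording for the meals: *Each volunteer receives both meals, so the meals are compared within subject. With 28 completers, a paired t-test at two-sided alpha 0.05 has at least 80% power for a 2.0-point difference in PPT if the SD of the within-subject difference is at most 3.64 points (30 completers: 3.78 points).* The correlations used in this review need not enter the protocol.
2. Put sincalide versus placebo on a within-subject basis too, and state the outcome scale and SD that apply on those days. If PPT as a percentage of energy intake is not defined there, do not carry the meal figures over.
3. Specify subject and period terms in the ANOVA, so that the analysis uses the pairing.

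Keep enrolment at 30. The cost is a few sentences, with no change to schedule or endpoints. The downside is a power statement that is conditional on a stated SD, and a sincalide statement that may need an SD the sponsor has yet to find.

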All blood samples will be drawn under sterile technique through an indwelling catheter using the Vacutainer® system (Becton Dickson and Co.). Serum and plasma aliquots will be stored at -80°C until analysis. Blood samples will be drawn according to the

following scheme during each metabolic chamber stay: -15', 0', 15', 30', 45', 60', 75', 90', 120', 150', 180', 240', 300', 360'.

The following laboratory parameters will be recorded: T4, T3, free T4, free T3, TSH, glucose, insulin, BAs, Ghrelin, CCK, GLP-1, and free fatty acids.

Genetic testing

DNA samples will be obtained from leukocytes obtained during the screening visit. Samples will be analyzed for the Thr92Ala and -258 A/G polymorphisms, and for subsequent screening of known mutations of genes involved in the energy, carbohydrate, thyroid hormone and glucose metabolism, as well as scanning for novel mutations in genes involved in these same metabolic pathways. Since these data do not currently have clinical relevance, study volunteers will not be notified of the results.

Laboratory testing

Screening tests (Chem 20, lipid panel, CBC with differential, TSH, HCG) will be performed in the Department of Laboratory Medicine (DLM). Genomic DNA will be isolated from peripheral mononuclear cells using the QIAmp® system (QIAGEN) in [name] laboratory. The following tests will be performed by the Department of Laboratory Medicine (DLM): Chem 20, insulin, cholesterol, HDL, triglycerides, free fatty acids, TSH, total and free T3, and total and free T4. Aliquots of serum and plasma will be also collected and stored at -80 C° for further analysis. GLP-1, CCK, and Ghrelin will be measured by immunometric assay in the clinical research core laboratory of NIDDK. Serum BAs (Cholic acid, Deoxycholic acid, Chenodeoxycholic acid, Total bile acids) will be measured by radio-immunoassay technique (Mayo Clinic).

Radiology studies

Right upper quadrant ultrasound to screen for the presence of gallstones will be performed at the screening visit. DEXA scan for body composition will be performed during hospital day #1 or #2 using the Metabolic Unit GE iDXA.

Statistical analysis

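### The stated blood volume (350 mL in one seven-day admission) and the stated 6 mL/kg cap cannot both be followed for eligible volunteers under 58.3 kg

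*Combined protocol and SAP*

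**What the plan says.** Study design and methods sets the number of stays and the period: "During a seven-day stay at the NIH, volunteers will undergo five 6-hour clinical and experimental observations in the metabolic chamber".

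Blood sampling, urine collection gives one list of times for every stay: "following scheme during each metabolic chamber stay: -15', 0', 15', 30', 45', 60', 75', 90', 120', 150', 180', 240', 300', 360" minutes. It states no volume.

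The Blood drawing paragraph under Possible Risks and Hazards gives the count, "Study subjects will undergo 5 venipunctures (14 blood draws during each metabolic chamber stay) during the study", then the volume, "Each blood drawing will be for 5 mL of blood", and then the limit, tied to NIH guidelines: "no more than 6 mL/Kg will be drawn from any study participants during a six-week period".

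The Inclusion and Exclusion Criteria admit adults of both sexes. The only body-size limit is BMI, which must be above 20 and below 27. No minimum weight is set.

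Blood is also taken at screening. Laboratory testing says "Screening tests (Chem 20, lipid panel, CBC with differential, TSH, HCG) will be performed", and Genetic testing says "DNA samples will be obtained from leukocytes obtained during the screening visit". No volume is given for either, nor is the interval between screening and admission.

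**The concern.** The volume and the limit stand in consecutive sentences, and both are meant to apply to every participant. The volume is a fixed number of millilitres, whereas the limit scales with body weight. They can agree only above some weight, and the eligibility criteria do not keep volunteers above it.

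For a lighter volunteer, staff cannot follow both figures. At stake are consistency on participant blood loss and the clarity of the sampling plan. The blood series carries the bile acid and thyroid hormone measurements. These serve the hormonal part of the first aim and the exploratory models in Statistical analysis. They also supply the serum bile acid changes in terms of which that section words the primary endpoint. Energy expenditure itself is measured by the chamber and does not depend on blood volume.

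**Working it through.** **Inputs**
- Stays: 5, within seven days (Study design and methods), so all fall inside one six-week window.
- Draws per stay: 14. The times listed in Blood sampling, urine collection number 14, which reproduces the 14 stated in the Blood drawing paragraph.
- Volume per draw: 5 mL (Blood drawing).
- Cap: 6 mL/kg in six weeks (Blood drawing).
- Body size: BMI above 20 and below 27 (Exclusion Criteria).
- Heights below are illustrative; the documents give none.

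**Total volume.** 14 × 5 mL = 70 mL per stay, and 5 × 70 = 350 mL over the admission. The 350 mL is not printed, but every factor is.

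**Threshold weight.** 350 / 6 = 58.33 kg. At 58.3 kg the cap is 349.8 mL, just short; at 58.4 kg it is 350.4 mL, which suffices.

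**Are such volunteers eligible?** BMI at 58.33 kg = 58.33 / height²:
- 1.55 m: 58.33 / 2.4025 = 24.3, so eligible volunteers with BMI above 20 and below 24.3 are under the threshold.
- 1.60 m: 58.33 / 2.56 = 22.8, so above 20 and below 22.8.
- 1.65 m: 58.33 / 2.7225 = 21.4, so above 20 and below 21.4.
- Upper height: √(58.33 / 20) = 1.71 m. With no screening blood counted, no eligible volunteer taller than this is affected.

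**Size of the excess**

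| Weight | Cap (6 × kg) | Excess over cap | Share of 350 mL | Cap / 70 draws |
|---|---|---|---|---|
| 56.3 kg (1.60 m, BMI 22: 22 × 2.56 = 56.32) | 337.9 mL | 12.1 mL | 3.5% | 4.83 mL |
| 55 kg | 330 mL | 20 mL | 5.7% | 4.71 mL |
| 50 kg | 300 mL | 50 mL | 14.3% | 4.29 mL |

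With BMI above 20, 55 kg is eligible only below √(55/20) = 1.66 m and 50 kg only below √(50/20) = 1.58 m, so the last row is toward the edge of the eligible range. The last column only locates the conflict: it lies in the nominal 5 mL, not in the 70 sampling times. It is not a proposed volume.

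**Screening blood.** The five venipunctures match the five stays, so the stated count leaves screening blood out. Its volume is not given. If 10, 20 or 40 mL (assumed) were drawn in the same six weeks, the threshold would be 360/6 = 60.0, 370/6 = 61.7 or 390/6 = 65.0 kg. The height above which nobody eligible is affected would be √(60.0/20) = 1.73, √(61.7/20) = 1.76 or √(65.0/20) = 1.80 m.

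**The case against.** The strongest reply is that the text already resolves the matter. The sentence with the cap opens with a contrasting however, so it reads as a general figure followed by an overriding limit. This stands as far as it goes. A reader might infer that the protocol plans to exceed its own limit, and the documents do not support that. But if the cap governs, the stated 5 mL at each of 70 draws still cannot be followed for these volunteers.

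A second reply is that nothing need be lost. This also stands. A reader might convert the excess into missed draws (20 mL at 5 mL each is 4 draws), but the list of times carries no volume, and all 70 times fit under the cap if less is taken at each. The documents give no assay volumes, so whether a smaller amount would cover the panels cannot be judged.

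Third, the missing detail may exist. The figure captioned "6-hour Metabolic Chamber stays, procedures and blood drawing protocol" is not shown in the text reviewed, and it may contain a rule for lighter volunteers. It therefore cannot be said that no such rule exists.

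Fourth, one could read the 5 mL as the amount per venipuncture, 25 mL in all, which would remove the conflict. That reading does not fit: the 5 mL sentence follows directly on a count of 14 draws per stay, and the samples are separately timed.

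A further tempting inference is that the shortfall would fall on the ursodiol stay, which comes last for everyone. If blood were drawn at the nominal volume until the cap was reached, a 50 kg volunteer would have used 4 × 70 = 280 mL after four stays, leaving 20 mL, or 4 of the 14 draws. Nothing in the visible text says the cap would be applied that way. It is a reason for care in the reconciliation, not a finding about the plan.

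**Conclusion.** The point holds as a clash between two stated figures. At the stated volume and count, the chamber stays alone take 350 mL, which exceeds the stated cap for any eligible volunteer under 58.3 kg. The excess is 12 mL at 56.3 kg, 20 mL at 55 kg and 50 mL at 50 kg. The 58.3 kg threshold and the 1.71 m height limit count no screening blood; both rise if any is drawn in the same six weeks.

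The result rests on reading 5 mL as the volume of each timed draw, which the wording supports. The documents give no weight distribution, so the number affected among the 30 planned volunteers is unknown. The finding does not extend to a planned breach, lost samples, a missing reduction rule or any effect on chamber-measured energy expenditure. Severity is minor: it is confined to lighter volunteers, modest in size and easy to correct.

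**What to change.** Reconcile four things so that the stated figures agree for every eligible volunteer: the volume per draw and number of draws (Blood sampling, urine collection; Blood drawing), the 6 mL/kg cap (Blood drawing), the eligible body sizes (Exclusion Criteria), and any screening blood taken in the same six weeks. Which of these should change is for the sponsor; no volume, limit or minimum weight is proposed here.

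However it is done, any adjustment should not fall unevenly on particular stays within a volunteer, so that bile acid and hormone comparisons between treatments rest on like sampling. If Fig. 2 already contains a suitable rule, a cross-reference in the Blood drawing paragraph would do.

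The text change is short. The cost depends on what is altered: a change to draw volume or count would need the laboratories to confirm that the assay panels and stored aliquots are still covered, and a change to eligible body size would affect recruitment.
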